5.3 Handling of Dropouts or Missing Data

Unless otherwise specified, missing data will not be imputed. Subjects who drop out will not be replaced and all available data will be used.

5.3.1 Diary Data

Daily diary entries to record bleeding/spotting/cramping by the subject are made directly onto paper CRFs and are, therefore, "self-sourcing" source data. If a subject does not bring the original (O) diary to the clinic visit, then the site will ask the subject to recall the data on a diary copy (C). The copy will be used until the original is returned at a following clinic visit.

If the original diary becomes available after the data from the copy have been entered into the study data base, the data base will be updated to include the original diary data along with the copy. The data base audit trail will reflect initial data entry from the copy followed by subsequent entry of the original. Diaries returned by the subject that include days when no information was obtained will have those data records included in the data base. However, no such blank records are in the data base for entire diary pages that may have not been returned, e.g., the subject may have returned diaries for March and May but never returned the April diary. In these cases, missing data are not part of the data base but are accounted for as blank records in the same manner as those which appear, essentially at random, within a returned diary. Since the diary day counting process for identification of 28-day cycles looks at each diary date record relative to the IUS insertion date, the presence of missing diary records will not affect this calculation. The extent and magnitude of missing diary records will be assessed and presented as part of overall diary results.

Diary numbers on CRFs will not be used; only the date information on the CRF will be used. If the date recorded does not exist, the data will not be included. If the subject never returns the original diary, the copy will be used for analyses. Duplicate diary records (e.g., an original and a clinic copy) for the same study day can appear in the study data base and should be handled as follows:

- If the diaries represent an original diary and a clinic copy diary, the original diary data will serve as the diary data of record
- If the diaries are submitted as duplicates of the same original or same clinic copy, the most recently submitted version will be used for analyses

Bleeding and cramping categories are listed below in order of increasing severity:

- Bleeding: None, Spotting, Light Flow, Normal Flow, Heavy Flow
- Cramping: None, Mild, Moderate, Severe

5.3.2 Bleeding and Cramping

For the categories of bleeding and cramping no imputation of data from the diaries will be done for missing data. For example, a subject with completely missing data for a particular diary day will be considered as having no reported bleeding or cramping for that day. Missing data for, say, bleeding alone will be considered as the subject having no reported bleeding for that day.

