8. DATA QUALITY CONTROL AND ASSURANCE

Electronic Case Report Forms (eCRFs) for this study will be designed and provided by [REDACTED]

[REDACTED] eCRFs will be completed by authorized study staff at each study location and transmitted to [REDACTED]. Daily diary entries by the subject will be entered into an eCRF by site staff. [REDACTED] will be responsible for data management of this trial, including quality checking of CRFs. In the event of incomplete or inconsistent data, requests for data correction will be sent to the sites for resolution. A complete audit trail of changes to the data will be maintained and available from the clinical trial database. Laboratory data (e.g., hemoglobin/hematocrit, ferritin, chemistry, quantitative hCG, urine pregnancy, Chlamydia, gonorrhea, FSH, TSH, PRL, vWF, ALT, AST) will be collected utilizing the site's local accredited laboratory (unless performing CLIA-waived tests). The site will enter the laboratory values for subjects in the clinical trial electronic database. The Data Management Plan will describe the quality checks that will be performed on the CRFs and the electronic data. CRFs and correction documentation will be converted to pdf format and bookmarked for indexing. Records retention for study data will be consistent with [REDACTED] standard procedures. Routine system backup and archiving will also be performed based on [REDACTED] standard procedures.

This study will be conducted in accordance with all applicable FDA guidances and regulations.

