13. APPENDIX B: SCHEDULE OF EVENTS ENROLLMENT AND FOLLOW-UP

ASSESSMENTS	ENROLLMENT	TREATMENT					7-DAY FU CONTACT ⁶	ADDITIONAL FOLLOW-UP ⁷
	VISIT 5	VISIT 6	CONTACT	VISIT 7	CONTACT	VISIT 8 or ED		
	IUS INSERT	DAY 28-42	DAY 50-56	DAY 85-89 ²	DAY 133-140	DAY 169-174 ²	7-10 DAYS AFTER IUS REMOVAL	AS NEEDED
Blood Pressure/Pulse	X	X		X		X		
Weight	X	X		X		X		
Medical History	X							
Urine Pregnancy Test	X	X		X		X		
Breast Exam						X		
Pelvic Exam	X					X		
Gonorrhea/Chlamydia	X ¹	X ¹		X ¹		X ¹		
Hemoglobin/Hematocrit, Ferritin	X			X		X ³		
Venous blood for AH Analysis				X		X		
Confirm Eligibility	X							
Instruct/Dispense Diaries	X	X		X				
Instruct/Dispense Sanitary Products	X	X		X				
Instruct/Dispense Collection Kit		X		X				
Collect Sanitary Products/Collection Kit/Assess for Compliance				X		X		
Collect Diary/Assess for Compliance	X	X		X		X		
VAS Questionnaire	X			X		X		
Insertion of IUS	X							
Review of Adverse Events	X	X		X		X	X	X
Review Concomitant Meds	X	X		X		X	X	X
Verify IUS Presence		X		X		X		
Removal of IUS							X ⁴	
Schedule Next Visit/Contact	X	X		X		X ⁵		
Remind when to collect Products			X		X			
Confirm Next Visit			X		X			

¹ Test indicated only if change in sexual partner

² Visit to occur ideally within the 5 day window but may be up to 21 days (V7 window Days 85-105; V8 window Days 169-189)

³ If not collected within 6 weeks

⁴ As applicable; subject may keep IUS if not contraindicated

⁵ If has IUS removed

⁶ For subjects with IUS removed

⁷ For ongoing IUS or IUS removal-related AEs

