9.3 Key Secondary Efficacy Variables

All key secondary outcomes will be summarized by descriptive statistics using the MITT Population except that the bleeding and/or spotting analyses will be summarized using both Safety and MITT Populations. The subgroup analysis of absolute change in the median MBL from baseline to End-of-study will assess differences for age, race/ethnicity, and BMI subgroups, no formal statistical testing will be performed.

Menstrual Blood Loss:

- Absolute change in baseline MBL to mid-treatment MBL (Cycle 3)
- Percent change from baseline MBL to mid-treatment MBL (Cycle 3)
- Absolute change from baseline to end of treatment (Cycle 6), including subgroup analysis for age, race/ethnicity, and BMI

- Percent change from baseline MBL to end of treatment MBL (Cycle 6)

Vaginal Bleeding Flow:

- Vaginal bleeding flow (none, spotting, and light, normal, or heavy flow [bleeding]) will be summarized based on the daily diary by incidence and duration of bleeding at each Cycle. Vaginal bleeding is recorded on the daily diary during the Screening Phase and baseline will be considered the cycle with the worst flow severity during the screening cycles.
 - Based on World Health Organization (WHO) terminology, bleeding and spotting are defined as:
 - Bleeding: any bloody vaginal discharge for which protection, such as pads is used
 - Spotting: any bloody vaginal discharge for which protection is not used; if spotting and bleeding occur on the same day, it is recorded as a bleeding day
 - Incidence of bleeding by 28-day cycle intervals post-insertion (none vs. spotting vs. bleeding; none vs. ≥ 1 day; 1-3, 4-7, >7, and >20 days; no bleeding vs. any bleeding) will be summarized
- Vaginal Bleeding Episodes
 - Based on the individual subject's daily diary of bleeding
 - A bleeding day is when sanitary protection is used
 - A bleeding episode is defined as light, normal or heavy bleeding during a minimum of one day as defined by a subject's subjective assessment
 - A bleeding-free day is defined as a day with either no bleeding or only spotting
 - A single bleeding episode will consist of all bleeding days separated by no more than one bleeding-free day. Separate bleeding episodes will consist of bleeding days separated by more than one bleeding-free day. An episode will be considered stopped with two consecutive bleeding-free days.

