- Bleeding will be summarized by the number and percentage of days with a particular pattern during each 28-Day interval after enrollment through Cycle 6 or IUS Discontinuation.
- Absolute changes and percentage changes from baseline to Cycle 3, from baseline to Cycle 6, and from Cycle 3 to Cycle 6 of the Treatment Phase will be calculated for the following bleeding pattern indices:
 - Total number of days of bleeding
 - Total number of days that include spotting or bleeding
 - Total number of days that include spotting only
 - Total number of bleeding episodes
 - The baseline numbers are the average of the Screening cycles evaluated

The subjective assessment of the impact of the LNG20 IUS on menstrual bleeding severity, dysmenorrhea, pelvic pain and daily activities will be assessed using a 10 cm Visual Analog Scale (VAS) questionnaire with appropriate questions. The VAS questionnaires will be completed and collected at baseline (Visit 5), and after 3 cycles (Visit 7) and 6 cycles (Visit 8):

- VAS scores for each question will be summarized for baseline, Cycle 3, and Cycle 6.
- VAS changes from baseline to mid-treatment (Cycle 3), from mid-treatment (Cycle 3) to end of treatment (Cycle 6) and from baseline to end of treatment (Cycle 6) will be summarized for each question.

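### Blank diary days are counted as days without bleeding or cramping, so the key secondary day counts can be too low and an unreturned cycle between returned diaries can score zero

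*SAP*

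**What the plan says.** SAP 5.3.2 says that bleeding and cramping diary data will not be imputed, and then illustrates this: "a subject with completely missing data for a particular diary day will be considered as having no reported bleeding or cramping for that day". A day on which only the bleeding item is blank is likewise taken as having no reported bleeding.

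SAP 5.3.1 extends this to whole diary pages that never came back. Its example is a month missing between two returned months, where "missing data are not part of the data base but are accounted for as blank records in the same manner" as blanks within a returned diary. It also promises that "The extent and magnitude of missing diary records will be assessed and presented as part of overall diary results".

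SAP 9.3 builds the bleeding-pattern indices as totals per cycle: days of bleeding, days of spotting only, days of either, and number of episodes. Changes between baseline, Cycle 3 and Cycle 6 in these measures are key secondary outcomes (Protocol 3.1.2 and 9.8). For the baseline, "The baseline numbers are the average of the Screening cycles evaluated". On episodes, "A bleeding-free day is defined as a day with either no bleeding or only spotting" and "An episode will be considered stopped with two consecutive bleeding-free days".

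SAP 5.5 numbers cycles by comparing each recorded diary date with the insertion date, and runs diary-based duration to the last recorded diary date. I found no minimum number of completed diary days in either document, and no sensitivity analysis for missing diary days.

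**The concern.** In a total of days, a day counted as having no reported bleeding contributes exactly what a true bleeding-free day contributes. The rule is presented as making no imputation, but in a count it acts as filling in zero. A woman whose diary for a cycle is lost can then be indistinguishable from a woman who did not bleed in that cycle, and the tables would not separate the two.

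At stake is the accuracy of the descriptive bleeding-pattern results. The same rule also feeds the cramping-day summaries in SAP 11.3.

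**Working it through.** The plan states no figure that depends on this rule, so there is nothing to reproduce. The check is on how the rule behaves. All inputs on bleeding and missingness are assumptions, because the documents give neither. I use 6 true bleeding days per cycle and no true change. The 85 women are the planned number of completers (Protocol 9.1).

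**1. Direction for a single count.** Scored days = true days minus the bleeding or spotting days that fall on blank days. Each such blank lowers the matching total by one; no blank can raise a day total. A blank day with spotting only lowers the spotting and combined totals, not the bleeding total.

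**2. A wholly blank cycle between returned diaries (for example Cycle 3).** With 28 blanks the cycle scores 0 days, an apparent change of -100% for that woman. For k such women among 85, mean = 6 x (85 - k)/85 and change = -k/85:

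| k | Mean days | Change |
|---|---|---|
| 2 | 5.86 | -2.4% |
| 5 | 5.65 | -5.9% |
| 10 | 5.29 | -11.8% |

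**3. Scattered blanks.** If a fraction p of days is blank at random, the expected count is 6 x (1 - p): 5.7, 5.4 and 4.8 days for p = 5%, 10% and 20%.

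**4. Change from baseline.** With blank fractions b in screening and t on treatment, the reported change is (1 - t)/(1 - b) - 1:
- 10% blank on treatment only: 0.90/1 - 1 = -10.0%
- 10% blank in both phases: 0.90/0.90 - 1 = 0
- 10% blank in screening only: 1/0.90 - 1 = +11.1%

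The sign depends on which phase has more blanks.

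**5. Episodes.** SAP 9.3 does not say whether a blank day is bleeding-free. If it is programmed that way, one blank inside a 6-day bleed leaves 1 episode of 5 counted days; two consecutive blanks in the middle give 2 episodes and 4 counted days; a fully blank bleed removes the episode. Enumerating all 2^6 = 64 blank patterns, the chance that a 6-day bleed is split is 0.7%, 2.6% or 8.8% at 5%, 10% or 20% random blanks. Episode counts can therefore move either way.

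**6. A blank final cycle.** SAP 5.3.1 with 5.3.2 points to zero. SAP 5.5, which stops at the last recorded diary date, points to a cycle that was not reached if no later entry exists. The text does not settle which applies.

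**The case against.** The strongest reply is that blanks should be few. At Visits 2 to 4 (Protocol 6.7.3.3, 6.7.3.5 and 6.7.3.7) staff review the diary for completeness and have the woman correct incomplete entries. At Visits 6 to 8 it is reviewed again (Protocol 6.9.1, 6.9.3 and 6.10; Appendix B, "Collect Diary/Assess for Compliance"). A forgotten diary is recalled onto a copy (SAP 5.3.1), and Protocol section 8 adds that "In the event of incomplete or inconsistent data, requests for data correction will be sent to the sites for resolution". The outcomes are descriptive, and missing records will be reported. All of this stands and limits the problem. None of it changes how a remaining blank is counted, and SAP 5.3.1 itself expects some pages never to return.

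Four stronger readings are tempting, and the documents do not support them:
- **The bias favours the device.** Screening diaries follow the same rule, so change from baseline can move either way (step 4).
- **A blank Cycle 6 always scores zero.** SAP 5.5 leaves this open, and a completer attends Visit 8, where the diary is collected and reviewed.
- **A blank screening cycle grossly distorts baseline.** Arithmetically, (6 + 0)/2 = 3 would turn no change into 6/3 - 1 = +100%, and (6 + 6 + 0)/3 = 4 into 6/4 - 1 = +50%. The review and correction at Visits 2 to 4 make a wholly blank screening cycle unlikely.
- **The primary outcome is contaminated.** SAP 5.3.3 bars imputing blood loss from diary data alone for a missed visit. Its zero-loss rule rests on amenorrhea reported on the blood-loss CRF, or on reported spotting or light bleeding without product use, not on a blank diary.

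**Conclusion.** The point holds for the descriptive key secondary day counts. The stated rule gives a count that is too low whenever a blank day had bleeding or spotting, and it allows an unreturned cycle between returned diaries to be scored as zero. A blank final cycle is an ambiguity between SAP 5.3 and 5.5. The effect on episodes rests on the inference that blanks would be programmed as bleeding-free.

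The size is unknown. The figures above show how the rule scales under assumed bleeding and blank rates; nothing in the documents supports 5 or 10 wholly blank cycles among 85 completers. The planned report of missing records lets a reader see how many blanks there are, but does not correct the totals.

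**What to change.** - **SAP 5.3.2:** treat unrecorded days as missing. Set the day and episode counts of any cycle with no diary data to missing, not zero, and say in SAP 5.5 that this includes a final cycle.
- **Completeness minimum:** summarise counts only for cycles that meet a pre-specified share of recorded days. For treatment cycles, 80% is one example: 0.8 x 28 = 22.4, rounded up to 23 of 28. For screening, apply a comparable share to a defined window, such as the first day of the collected menses to the day before the next menses or IUS insertion, whichever comes first. Insertion can occur at any point in the cycle (Protocol 6.8.1).
- **Episodes:** do not let blank days alone end an episode. Where two or more consecutive blanks leave the count unclear, set it to missing.
- **Percentage of days:** reconcile SAP 5.2.1, which generally drops missing values from denominators, with 5.3.2. Show blank days as a separate not-recorded category.
- **Sensitivity tables:** keep the as-written count. Use recorded-day denominators or scaling only here, since both give the same artefact. If 5 dry baseline days are blank, 6 x 28/23 = 7.30, and a complete treatment cycle of 6 days then reads 6/7.30 - 1 = -17.9%. As percentages of days, 6/23 = 26.1% against 6/28 = 21.4% is also -17.9%.

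The cost is SAP wording and a short derivation; the extent of missing records is already to be presented. Some cycles drop out of the descriptive summaries. In a cycle that meets the minimum the day count is the same as under the present rule, so it can still be understated by up to 28 - 23 = 5 days. The gain is that empty and largely empty cycles no longer pass as low counts.

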5.3.3 Missing Data for MBL

- A MBL assessment by AH may not be collected for Treatment Phase Cycle 3 and Cycle 6 in which a subject reported being amenorrheic (no spotting/bleeding) for the 28-day collection interval on the CRF for AH Menstrual Blood Loss Assessment; in this case the corresponding MBL value will be set to 0 mL. Additionally, the participant may report spotting only or light bleeding on her diaries with no feminine hygiene products used; in this case the corresponding MBL value will be set to 0 mL
- For a Treatment Phase missed Visit 7 (Cycle 3) or missed Visit 8 (Cycle 6), no imputation of MBL from diary data alone will be conducted.
- For the evaluations of MBL, the last observation carried forward (LOCF) method will be used for imputation. If MBL data in Cycle 3 are available but no MBL data in Cycle 6 are available or Cycle 6 is invalid, then MBL data in Cycle 3 will be used as End of Study MBL.
- Additional imputation method(s) might be explored for sensitivity analysis when deemed necessary

5.3.4 Missing Adverse Event Start and Stop Dates

For adverse events (AE), the following rules for imputing values for missing start and stop dates are used:

- If the AE start date field includes a SAS missing value (e.g., .N) or is completely missing, the start date is set to the IUS insertion attempt date. This conservatively assumes that the AE began on the same date when insertion was first attempted
- If the AE start date field is missing day only, set it equal to the first day of the recorded month and year
- If the AE start date field is missing day and month only, set it equal to the first day of January of the recorded year.
- Any resultant imputed AE start date that is earlier than the IUS insertion attempt date is set equal to the IUS insertion attempt date. This also conservatively assigns the AE as having occurred on the same date as the IUS insertion attempt.
- If the AE stop date is completely missing, the event will be noted as “Continuing” in the stop date column in the AE listings.
- If the AE stop date field is missing day only, set it equal to the 15th day of the recorded month and year.

- If the AE stop date field is missing day and month only, set it equal to the 31st day of December of the recorded year.
- If the AE stop date field is missing month only, set it equal to December of the recorded year.
- A resultant imputed AE stop date that is earlier than the AE start date is set equal to the AE start date. This ensures that all AEs have a minimum duration of one day.

5.3.5 Missing Concomitant Medication Start and Stop Dates

For concomitant medications (CM), the following rules for imputing values for missing start dates and stop dates are used:

- If the CM start date field includes a SAS missing value or is completely missing, the start date is set to the IUS insertion attempt date.
- If the CM start date field is missing day only, set it equal to the first day of the recorded month and year.
- If the CM start date field is missing day and month only, set it equal to the first day of January of the recorded year.
- If the CM stop date field includes a SAS missing value or is completely missing and the CM is not ongoing, the stop date is set to the last date of known product use.
- If the CM stop date field is missing day only, set it equal to the 15th day of the recorded month and year.
- If the CM stop date field is missing day and month only, set it equal to the 31st day of December of the recorded year.
- If the CM stop date field is missing month only, set it equal to December of the recorded year.
- Any imputed CM stop date that is before the insertion attempt date implies the CM was a Pre-Trial Medication. Any medication started on or after the insertion attempt date or any medication started before insertion but ending on or before the last known date of product use is a Concomitant Medication.

5.3.6 Missing Dates for Other Events, Including Date of IUS Expulsion/Removal

For missing dates of other events, any date that is completely missing or contains the year only will be set to the date of the subject's last clinic visit. If a month and year are recorded but the day is unknown, the day will be set to the first day of the month. If this results in an imputed date that is earlier than the last clinic visit, the date will be set to the date of the last clinic visit.

5.4 Standard Calculations

Variables requiring calculation will be derived using the following formulas:

- **Study day** – For a given date (*date*) on or after successful IUS insertion (*iusindt*), study day is calculated as:

$$\text{Study day} = \text{date} - \text{iusindt} + 1$$

For a given date (*date*) prior to successful IUS insertion (*iusindt*) or for subjects with failed insertion, study day is calculated as:

$$\text{Study day} = \text{date} - \text{iusindt}.$$

The day of successful IUS insertion is Study Day 1 and the day prior to IUS insertion is Study Day -1. There is no Study Day 0

Months – A duration expressed in months is calculated as the number of completed calendar months plus the proportion of any partial month completed. A month is calculated using the following formula: Duration in months = $(\text{date2}-\text{date1})/30.4$

- **Years** - A duration expressed in years between one date (*date1*) and another later date (*date2*) is calculated using the formula noted below:

$$\text{Duration in years} = (\text{date2}-\text{date1})/365.25$$

- **Age** - Age is calculated as the number of years from the date of birth (*DOB*) to the IUS insertion attempt date (*iusindt*). For displaying a subject's age, the following formula is used:

$$\text{Age (years)} = \text{floor}(\text{insertion attempt date} - \text{birthdate})/365.25$$

- **Body Mass Index (BMI)** - BMI is calculated using height (in cm) and weight (in kg) at Screening Visit 1:

$$\text{BMI (kg/m}^2\text{)} = \text{weight (kg)} / [\text{height (cm)} / 100]^2$$

- **Cycles of Use** – Cycles are calculated using the date the IUS was expelled/removed (from the IUS Discontinuation CRF). Total use duration expressed as the number of 28-day cycles is defined as IUS expulsion/removal date or date of Visit 8 - date of

IUS insertion ($i_{usindt}+1)/28$. If re-insertion for expulsion takes place, the last IUS expulsion/removal date or date of Visit 8 is used. If the expulsion/removal date is unknown then:

- Subjects who are still on treatment will have their last known date of product use used in the cycle calculations in lieu of an IUS expulsion/removal date or date of Visit 8, derived as follows: The last known date of product use will be the last date of on-study contact with the subject where she reported that the IUS is still in place
- If, during on-study contact with the subject she reports that the IUS is no longer in place, the date of reported expulsion/removal if known, or if unknown the date of contact minus 1 day, will be used as the last date associated with IUS use.
- In the cases of subjects who are lost to follow-up or withdraw consent prior to Visit 8 and a last contact date is available, the last contact date- date of insertion ($i_{usindt}+1)/28$ will be used. If not contact date after insertion is available then date of IUS insertion + 1 day will be used as the last date associated with IUS use.

Similarly, for subjects who had a successful IUS insertion but who have not yet had any post-insertion data (e.g., Visit 6, Visit 7, Visit 8, unscheduled visit) retrieved at the site which could be used to directly calculate duration of use, the IUS insertion date +1 day will be used as the last date of IUS use for the purpose of analysis. For the summary of duration of product use, all subjects with ≥ 1 days of product use, as defined in this section, will be included in the calculations.

5.5 28-Day Cycles of Use Calculation

In addition to the calculation of 28-day cycles based on last date of IUS use as described in [Section 5.4](#), each recorded diary date between the IUS insertion date and the last calculated date of product use, inclusively, is compared to the IUS insertion date in order to calculate cycle number and day. Duration of use expressed as the number of 28-day cycles is then calculated as the maximum duration (ceiling value) between the IUS insertion date and last recorded diary date.

